13. Radiographic evidence of intratumoral cavitation, encasement, or invasion of a major blood vessel. Additionally, the degree of proximity to major blood vessels should be considered for exclusion because of the potential risk of severe hemorrhage associated with tumor shrinkage/necrosis after lenvatinib therapy.
14. History of ifosfamide-related Grade  $\geq 3$  nephrotoxicity or encephalopathy.
15. Evidence of clinically significant disease (eg, cardiac, respiratory, gastrointestinal, renal disease) that in the opinion of the investigator(s) could affect the subject's safety or interfere with the study assessments.

16. Known to be human immunodeficiency virus (HIV) positive. Note: HIV testing is required at screening only when mandated by local health authority.
17. Known active Hepatitis B (eg, HBsAg reactive) or Hepatitis C (eg, HCV RNA [qualitative] is detected). Note: Testing for Hepatitis B or Hepatitis C is required at screening only when mandated by local health authority.
18. Females who are breastfeeding or pregnant at Screening or Baseline (as documented by a positive beta-human chorionic gonadotropin [ $\beta$ -hCG]) (human chorionic gonadotropin [hCG]) test with a minimum sensitivity of 25 IU/L or equivalent units of  $\beta$ -hCG /hCG]. A separate baseline assessment is required if a negative screening pregnancy test was obtained more than 72 hours before the first dose of any study drug.
19. Females of childbearing potential\* who:
  - Do not agree to use a highly effective method of contraception for the entire study period and for 28 days after lenvatinib discontinuation or 12 months after etoposide and ifosfamide discontinuation, ie:
    - total abstinence (if it is their preferred and usual lifestyle)
    - an intrauterine device (IUD) or intrauterine hormone-releasing system (IUS)
    - A contraceptive implant
    - an oral contraceptive\*\* (with additional barrier method)
  - OR
  - Do not have a vasectomized partner with confirmed azoospermia.For sites outside of the EU, it is permissible that if a highly effective method of contraception is not appropriate or acceptable to the subject, then the subject must agree to use a medically acceptable method of contraception, ie, double-barrier methods of contraception such as condom plus diaphragm or cervical/vault cap with spermicide.

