- \* All post pubertal females will be considered to be of childbearing potential unless they have early menopause (amenorrheic for at least 12 consecutive months, in the appropriate age group, and without other known or suspected cause) or have been sterilized surgically (ie, bilateral tubal ligation, total hysterectomy, or bilateral oophorectomy, all with surgery at least 1 month before dosing), or are pre-menarcheal (Tanner Stage 1-3).
- \*\*Must be on stable dose of the **same** oral hormonal contraceptive product for at least 4 weeks before dosing with study drug(s) and for the duration of the study.
20. Males who have not had a successful vasectomy (confirmed azoospermia) or if they and their female partners do not meet the criteria above (ie, not of childbearing potential or practicing highly effective contraception throughout the study period and for 28 days after lenvatinib discontinuation or 6 months after discontinuation of etoposide and ifosfamide). No sperm donation is allowed during the study period and for 28 days after lenvatinib discontinuation or 6 months after discontinuation of etoposide and ifosfamide.
21. A contraindication to any of the study drugs (lenvatinib, ifosfamide, and etoposide) per local prescribing information.

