**Table 5 Schedule of Assessments in Study E7080-G000-230 – Randomization Phase**

Phase	Prerandomization		Randomization a (All cycles are 21 days in duration)																		
Period	Screening b	Baseline c	Treatment d																Off-Tx	Follow-up	
Visit	1	2	3	4	5	6	7	8	9	10	11	12	13	14	15	16	17	18+			
Cycle			Cycle 1			Cycle 2			Cycle 3			Cycle 4			Cycle 5			Cycle 6-X			
Day	-28 to -2	-1	1	8	15	1	8	15	1	8	15	1	8	15	1	8	15	1			
Procedures/Assessments																					

then the subject does not need a reassessment at the Off-treatment Visit. X-ray of only 1 leg is required, and if reassessment is needed at the Off-treatment Visit, the x-ray must be performed on the same leg as at Screening. Tibial growth plate x-rays will be optional for Germany. A dental examination by a qualified healthcare professional should be conducted per local institutional guidelines at baseline (C1D1±4 weeks), and thereafter per local standard of care (but no less than annually), and as part of the Off-treatment assessment. If the most recent dental examination is within 6 months prior to the Off-treatment Visit, the dental exam is not required. Post-baseline dental exams are not required for subjects for whom permanent teeth (excluding third molars) are evaluated to be fully erupted at baseline.

- t. Tanner Staging is only required for female subjects  $\geq 8$  years old, and male subjects  $\geq 9$  years old. Tanner Stage will be assessed at the Baseline Visit, at the Off-treatment Visit, and annually thereafter during the Post-treatment Follow-up. Tanner Staging is not required once pubertal development is complete (ie, Tanner Stage 5).
- u. Every effort should be made to administer the PedsQL questionnaires as soon as possible after the decision to discontinue study treatment is made.
- v. Optional blood samples may be collected only from subjects in Arm A at the Baseline Visit, C1D15, Day 1 of Cycles 2, 4, and 6, for assessment for blood serum sample to measure factors implicated in angiogenesis. Pharmacodynamic sampling should not be performed for any subject with a body weight  $< 16$  kg (please see [Section 9.5.1.3.1](#)).

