- n. Prior to optional lenvatinib crossover, baseline tumor assessment must be re-established (i.e., new tumor assessment scans performed), unless the last assessment was performed within 4 weeks prior to Cycle 1 Day 1 of the crossover treatment. Tumor assessments may be performed as clinically indicated as per the institutional guidelines (but no less frequently than every 12 weeks), following the prevailing local standard of care. The scans will no longer be required to be sent to the ICL.
- o. Brain CT with contrast or MRI pre- and post- gadolinium contrast will be performed as clinically indicated as per the institutional guidelines, following the prevailing local standard of care.

- p. Height will be assessed at the Baseline Visit, Day 1 of every 4 cycles during treatment, at the Off-treatment Visit and every 3 months during the Post-treatment Follow-up. Assessment of height in Post-treatment Follow-up is not required once pubertal development is complete.
- q. Tanner Staging is only required for female subjects  $\geq 8$  years old, and male subjects  $\geq 9$  years old. Tanner Stage will be assessed at the Baseline Visit, at the Off-treatment Visit, and annually thereafter during the Post-treatment Follow-up. Tanner Staging is not required once pubertal development is complete (i.e. Tanner Stage 5).
- r. Survival data will be collected every 3 months for up to 2 years as per the protocol. All anticancer therapies will be collected.
- s. Concomitant medications will be recorded throughout the study and for 30 days after last dose. All anticancer therapy will be recorded until time of death or termination of Survival Follow-up.
- t. All AEs, including SAEs will be recorded from the date of signed informed consent, throughout the study, and for 30 days after last dose. SAEs irrespective of relationship to study treatment must be reported as soon as possible but not later than 24 hours.

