### **Girls Tanner Stage progression scale**

#### **Breast:**

1= The nipple is raised a little. The rest of the breast is still flat.

2= This is the breast bud stage. In this stage, the nipple is raised more than in stage 1. The breast is a small mound. The areola is larger than stage 1.

3= The breast and areola are both larger than in stage 2. The areola does not stick out away from the breast.

4= The areola and the nipple make up a mound that sticks up above the shape of the breast.  
NOTE: This stage may not happen at all for some girls. Some girls develop from stage 3 to stage 5 with no stage 4

5= This is the mature adult stage. The breasts are fully developed. Only the nipple sticks out in this stage. The areola has moved back in the general shape of the breast.

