**Pubic Hair:**

1= There is no pubic hair at all.

2= There is a little soft, long lightly-colored hair. This hair may be straight or a little curly.

3= The hair is darker in this stage. It is coarser more curled. It has spread out and thinly covers a bigger area.

4= the hair is now as dark, curly, and course as that of an adult female. The area that the hair covers is not as big as that of an adult female. The hair has NOT spread out to the legs.

5= The hair is now like that of an adult female. It covers the same area as that of an adult female. The hair usually forms a triangular (V) pattern as it spreads out to the legs.

\*Adapted from: Morris, N.M., and Udry, J.R., (1980). Validation of a Self-Administered Instrument to Assess Stage of Adolescent Development. *Journal of Youth and Adolescence*, Vol. 9, No. 3: 271-80.

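### The childbearing-potential definition does not clearly cover a girl past menarche but still in puberty, and no scheduled item on treatment asks about menarche (minor safety point)

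*Protocol*

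**What the plan says.** Protocol Section 9.3.2, exclusion criterion 19, sets the rule: "All post pubertal females will be considered to be of childbearing potential unless they have early menopause". Surgical sterilization is a further exception, and the last one reads "or are pre-menarcheal (Tanner Stage 1-3", with the bracket closing there. The Synopsis has the same wording.

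Females of childbearing potential must agree to highly effective contraception "for the entire study period and for 28 days after lenvatinib discontinuation or 12 months after etoposide and ifosfamide discontinuation".

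Section 9.5.1.4.7 (Pregnancy Test) refers back to this definition. Table 5 footnote e, Table 6 footnote b and Table 7 footnote k schedule tests on Day 1 of each cycle (from Cycle 2 in Tables 5 and 7) and at the Off-treatment Visit, for women of childbearing potential only.

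On pubertal staging, Table 5 footnote t says "Tanner Stage will be assessed at the Baseline Visit, at the Off-treatment Visit, and annually thereafter during the Post-treatment Follow-up", and that "Tanner Staging is not required once pubertal development is complete (ie, Tanner Stage 5". Table 6 footnote n and Table 7 footnote q match it on both points. In Appendix 9 the girls' scale scores breast and pubic hair only; breast Stage 5 is described as "This is the mature adult stage. The breasts are fully developed" and pubic hair Stage 5 as "The hair is now like that of an adult female".

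**The concern.** The definition starts from females who are past puberty and then exempts girls who have not had a first period. Those two ideas do not meet. Girls who are past menarche but still in puberty lie between them, and the Stage gloss stands in for menarche on a scale that does not record it. Two sites could classify the same girl differently.

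The second issue is timing. A girl may enter before menarche and reach it on treatment. If nothing prompts the site to ask, she comes under pregnancy testing and contraception only if the site learns of the change some other way. At stake is exposure of a pregnancy to ifosfamide, etoposide and lenvatinib, the last of which has no fixed end in Arm A (Section 9.4.1), and withdrawal of the subject under Section 9.5.4.2.

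**Working it through.** **Step 1. Apply the definition to four girls.** The Protocol links completed puberty to a Tanner Stage only through the staging footnotes (Table 5 t, Table 6 n, Table 7 q), where it is Stage 5. Those footnotes say when staging may stop; they do not define the term used in criterion 19. The literal column borrows their meaning because no other is given.

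| Girl | In the base group, read literally? | Exempt? | Result |
|---|---|---|---|
| Stage 1 to 3, before menarche | No | Yes | Not of childbearing potential; clear |
| Stage 3 or lower, after menarche | No | By the gloss yes, by the noun no | Unclear |
| Stage 4 | No | By the gloss no; by the noun only if before menarche | Unclear |
| Stage 5, after menarche | Yes | No | Of childbearing potential; clear |

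Read literally, the pre-menarcheal exemption removes nobody, because a pre-menarcheal Stage 1 to 3 girl was never in the base group.

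**Step 2. Look for an item that would update the classification on treatment.**

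- Tanner Stage: Baseline, Off-treatment, then annually. None during treatment cycles in Tables 5, 6 or 7.
- Pregnancy test: every cycle, but only for those already classed as of childbearing potential. It uses the classification and does not ask for a new one.
- Physical examination on Day 1 of each later cycle (Table 5 footnote g): the contents listed in Section 9.5.1.1.3 include no pubertal item, and a urogenital examination is needed only for symptoms.
- Crossover Baseline (Table 7 footnotes b and q): Arm B subjects who cross over have safety eligibility and Tanner Stage checked again, then nothing further until the crossover Off-treatment Visit.
- Contraception: framed as an entry criterion. No text says it begins when a girl's status changes.

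If lenvatinib lasts to the median PFS assumed for Arm A in Section 9.7.2, the interval between Tanner assessments is 8.75 x 30.44 = 266 days, and 266 / 21 = about 12.7 cycles. For chemotherapy alone it is 5 x 21 = 105 days, plus up to 30 days to the Off-treatment Visit.

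**Step 3. Scale.** The Protocol gives neither the female share nor pubertal status, so this is illustration only. Assumed: 2% to 10% of each 36-subject arm are pre-menarcheal girls; time to menarche is uniform over the next 6 years (low case) or 2 years (high case); treatment lasts 8.75 months in Arm A and 105 / 30.44 = 3.45 months in Arm B; crossover treatment is not counted.

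- Pre-menarcheal girls per arm: 36 x 0.02 = 0.72 to 36 x 0.10 = 3.6.
- Low: Arm A 0.72 x 8.75 / 72 = 0.09; Arm B 0.72 x 3.45 / 72 = 0.03; total 0.12.
- High: Arm A 3.6 x 8.75 / 24 = 1.31; Arm B 3.6 x 3.45 / 24 = 0.52; total 1.83.

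The contraception requirement outlasts treatment. With five completed cycles and deaths ignored, chemotherapy plus 12 months is 3.45 + 12 = 15.45 months in each arm. That gives 2 x 0.72 x 15.45 / 72 = 0.3 to 2 x 3.6 x 15.45 / 24 = 4.6 girls in total.

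**The case against.** The strongest reply is that the definition, read as a whole, gives almost the intended rule. A girl past menarche is not pre-menarcheal, so she is not exempt; a Stage 4 girl lies outside the bracket, so she is not exempt either. The exemption would have no purpose unless the opening phrase was meant to reach girls already in puberty. That is fair, and it makes the wording defect one of drafting. It stands as a defect because the opening phrase, taken at its word, still leaves these girls out.

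A reader might infer that status is settled once, at Baseline, and that the Protocol therefore leaves such girls unprotected. The documents do not support that. Nothing freezes the classification, Section 9.5.1.4.7 sends the site back to the definition, and tests are due every cycle, so a careful site could reclassify a girl at any Day 1 visit. Subjects are seen often, and crossover subjects are formally rechecked once. What is missing is a prompt, not a rule against reclassifying. Counselling at consent cannot be judged either, since consent pages are not in the public copy.

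It is also fair that the counts above rest on assumed inputs, that the high case stacks the largest share on the shortest window, and that they count girls reaching menarche, not harm. Harm further requires that the site does not notice, that no contraception is used, and that conception occurs.

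**Conclusion.** The point holds as a minor, cheap safety improvement. The definition does not clearly cover a girl who has reached menarche without completing puberty. Between Baseline and Off-treatment no scheduled item elicits menarche (crossover Baseline restages and rechecks eligibility once), and no text starts contraception when it occurs.

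The number affected cannot be derived from the Protocol and is probably very small. Section 7.1 puts peak incidence at 15 to 19 years and median age at diagnosis at 20, although entry is open from age 2 and at least 36 of about 72 subjects must be under 17. The range of 0.1 to 1.8 girls on randomized treatment depends entirely on the assumptions in the working. The primary PFS analysis, the 38 events and the sample size are untouched. It would go too far to conclude that the Protocol exempts menarcheal girls from contraception or that pregnancies should be expected.

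**What to change.** Define childbearing potential as any female who has reached menarche or, from Baseline on, whose recorded Tanner Stage is 4 or higher, unless surgically sterilized or in early menopause. The Stage limb can only work from Baseline because staging is first scheduled there. Delete the post-pubertal opening and the Stage 1 to 3 gloss.

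Record menarche at Screening. Ask pre-menarcheal girls again on Day 1 of each cycle, at the Off-treatment Visit, and at follow-up contacts through 12 months after the last ifosfamide and etoposide dose, or 28 days after the last lenvatinib dose if that is later. The follow-up part matters because Arm B is off treatment after five cycles while the contraception requirement continues.

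Once menarche is reported, start pregnancy tests while the girl is on treatment, and start contraception by a method that does not depend on 4 weeks of stable oral-contraceptive use before dosing, a condition that a girl already on treatment cannot meet.

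Text to change: criterion 19 in the Synopsis and Section 9.3.2, the pregnancy-test paragraph of Section 9.5.1.4.7, Table 5 footnote e, Table 6 footnote b and Table 7 footnote k, plus a line for the follow-up question. The cost is one question at existing contacts and a few extra pregnancy tests, including in Stage 4 girls. No Tanner staging is added.

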### 9.3.3 Removal of Subjects From Therapy or Assessment

Subjects will continue to receive study treatment until any of the following occur:

- Progressive disease (as confirmed by IIR\*)
- Unacceptable toxicity
- Subject request
- Withdrawal of consent
- Termination of the study by the Sponsor

The investigator may discontinue treating a subject with study treatment or withdraw the subject from the study at any time for safety or administrative reasons. The subject may decide to discontinue study treatment or withdraw from the study at any time for any reason. The reason for discontinuation will be documented. If a subject discontinues study treatment, the subject will enter the Follow-Up Period and complete protocol-specified off-treatment visits, procedures, and survival follow-up unless the subject withdraws consent. The investigator should confirm whether a subject will withdraw from study treatment but agree to continue protocol-specified, off-treatment study visits, procedures, and survival follow-up, or whether the subject will withdraw consent. If a subject withdraws consent, the date will be documented in the source documents.

During the Follow-Up Period, subjects who have discontinued study treatment without progression should have disease assessments as per the appropriate tumor assessment schedule in [Table 5](#) and [Table 6](#) from the date of the last assessment until PD is documented or another anticancer therapy is initiated. After data cutoff for the primary analysis, tumor assessments may be performed as clinically indicated per institutional guidelines (but no less frequently than every 12 weeks), following the prevailing local standard of care, and IIR confirmation of radiographic evidence of PD will not be required.

All subjects will be followed for survival for up to 2 years after end of treatment for a subject, except where a subject withdraws consent or the sponsor chooses to halt survival follow-up after completion of the primary study analysis.

\*Confirmation of disease progression by IIR is only required during the Randomization Phase.

## 9.4 Treatment(s)

### 9.4.1 Treatment(s) Administered

Lenvatinib will be provided by Eisai as hard capsules containing 1, 4, or 10 mg lenvatinib. An extemporaneous suspension of lenvatinib capsules should be used for subjects unable to swallow capsules, as detailed in the Pharmacy Manual.

**Test Arm (Arm A): Lenvatinib + Ifosfamide + Etoposide**

Lenvatinib 14 mg/m^2, orally administered once daily in each 21-day cycle.

Lenvatinib is provided as hard capsules containing 1 mg, 4 mg, or 10 mg lenvatinib. An extemporaneous suspension of lenvatinib capsules should be used for subjects unable to swallow capsules. After adjustment for body surface area (BSA), the daily dose cannot exceed 24 mg QD.

Ifosfamide 3000 mg/m^2/day, IV, for 3 consecutive days (Day 1 to 3), every 21 days, for a maximum of 5 cycles.

Etoposide 100 mg/m^2/day, IV, for 3 consecutive days (Day 1 to 3), every 21 days, for a maximum of 5 cycles.

Treatment with lenvatinib will continue in 21-day cycles after chemotherapy is discontinued, until disease progression, development of unacceptable toxicity, subject request, withdrawal of consent, or discontinuation of study by the sponsor. In case the study is discontinued by the sponsor, the sponsor will provide study drug (outside the study) for subjects who have not met the criteria for study drug discontinuation.

**Control Arm (Arm B): Ifosfamide + Etoposide**

Ifosfamide 3000 mg/m^2/day, IV, daily for 3 consecutive days (Day 1 to 3), every 21 days, for a maximum of 5 cycles.

Etoposide 100 mg/m^2/day, IV, daily for 3 consecutive days (Day 1 to 3), every 21 days, for a maximum of 5 cycles.

Before dose administration on Day 1 of each cycle and prior to a change in dose due to dose reduction, the amount of lenvatinib needed for each subject must be calculated as follows:

$$\text{Scheduled dose (mg/m}^2\text{)} \times \text{body surface area (BSA) (m}^2\text{)} = \text{lenvatinib dose (mg)}$$

Body surface area (BSA) will be calculated using the method that is accepted and customarily used by the clinical site. BSA must be calculated on Day 1 of each cycle based on the subject's current height and body weight. BSA will be used to determine the amount of lenvatinib for each subject. BSA should not be corrected for amputation. The dose should be rounded to the nearest whole number. After adjustment for BSA, the daily dose of lenvatinib should not exceed 24 mg daily.

Subjects will receive study treatment as continuous 21-day cycles in both treatment arms. Treatment cycles will be counted continuously regardless of dose interruptions. If chemotherapy administration is precluded on Day 1 of a treatment cycle, the subject may resume treatment once recovered at the discretion of investigator. Subsequent chemotherapy will be administered every 21 ( $\pm 1$ ) days starting from the timepoint it was resumed.

**Optional Lenvatinib Crossover (for Subjects in Arm B Only):**

Subjects in Arm B with disease progression per RECIST 1.1 may be eligible for optional treatment with lenvatinib±chemotherapy. Please see [Section 9.1.4](#) for further details.

#### 9.4.1.1 Lenvatinib Dose Reduction and Interruption Instructions

Adverse events will be graded using CTCAE version 5.0.

Dose reduction and interruptions for subjects who experience lenvatinib related toxicity will be managed as described in [Table 1](#).

The starting dose of lenvatinib is 14 mg/m^2. Dose reductions occur in succession based on the previous dose level. Each dose level reduction is a 20% reduction from the previous dose.

Once the study drug dose level has been reduced, it may not be increased at a later date, unless the dose was mistakenly decreased; in this situation, the sponsor's approval is required to increase the dose.

Refer to the subsections below for management of hypertension, posterior reversible encephalopathy syndrome/reversible posterior leukoencephalopathy syndrome (PRES/RPLS), proteinuria, hepatotoxicity, thromboembolic events, hypocalcemia, gastrointestinal symptoms and acute abdominal pain, and hemorrhage, as appropriate, before consulting the dose modification table below.

